5.3 Handling of Missing Data and Outliers

5.3.1 Safety

Generally, no replacement will be done for safety missing data and outliers. In all subject listings, partial and missing data will be clearly indicated as missing.

5.3.1.1 Immediate

For unsolicited non-serious systemic AEs, a missing response to the "Immediate" field is assumed to have occurred after the 30-minute surveillance period and will not be imputed.

5.3.1.2 Causal Relationship

By convention, all events reported at the injection site (either solicited or unsolicited) will be considered as related to the administered product and then referred to as reactions. In a same way, all solicited systemic events pre-listed in the CRF are also considered as related to vaccination and will be considered as reactions.

- For unsolicited systemic AE, missing relationship will be considered as related to study vaccine at the time of analysis.
- The missing relationship to study procedures for SAEs will not be imputed.

5.3.1.3 Intensity

For solicited reactions, missing intensities will be handled as described in Section 4.4.1.1.1. For unsolicited AEs, missing intensities will remain missing and will not be imputed.

5.3.1.4 Start Date and End Date

Missing or partially missing start dates or end dates for unsolicited AEs (including SAEs) will remain missing and not be imputed. If the start date is missing or partially missing, the time of onset will be considered to be missing. Nevertheless, unsolicited AEs with missing time of onset will be included in analyses according to the last vaccination (computed according to the Section 4.4.1.2.3). If either the start date or end date is missing or partially missing, the duration will be considered missing.

Missing or partially missing end dates for ongoing solicited AEs will remain missing and not be imputed.

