4.4.1.2.4 Time of Onset

Time of onset is derived from the start date of the unsolicited AE provided in the clinical database and the date of last vaccination as described in Section 4.4.1.2.3:

Time of Onset = start date of the unsolicited AE - date of last vaccination before the unsolicited AE

The time of onset is considered as missing only if one or both dates are missing or partially missing.

The unsolicited AEs will be analyzed "Within 30 days" after each vaccination, which corresponds to AEs with a time of onset between 0 and 30 days after each vaccination or missing onset date. An AE with missing time of onset will be considered to have occurred just after the last vaccination (computed according to the Section 4.4.1.2.3), so will be included in these tables.

Time of onset period is displayed as D0-D3, D4-D7, D8-D14, D15 or later, and Missing.

Note: Unsolicited AEs that occurred before vaccination (negative time of onset) or with onset higher than defined above (e.g, >30 days after each vaccination for non-serious AE) will not be included in analysis, but will be listed separately.

4.4.1.2.5 **Duration**

Duration is derived from the start and end dates of the unsolicited AE:

Duration = End date of unsolicited AE - start date of unsolicited AE + 1.

The duration is considered as missing only if one or both of the start and end dates of the unsolicited AE is missing or partially missing.

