4.4.1.2.6 Serious Adverse Events

An event will be considered as a serious event if "Yes" is checked for "Serious" in the CRF.

SAEs will be analyzed throughout the study using the following periods:

- Within 7 days after vaccination
- Within 30 days after vaccination
- During the study (i.e., all SAEs occurred during the study)

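### A partly known AE start date is handled as wholly missing, so an event whose recorded month proves onset after Day 30 still enters the 30-day tables, and the 7-day SAE and AESI periods have no rule for missing onset

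*SAP*

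**What the plan says.** SAP 5.3.1.4 covers unsolicited AEs, SAEs included, and puts partial dates and absent dates under one rule: "Missing or partially missing start dates or end dates for unsolicited AEs (including SAEs) will remain missing and not be imputed". The consequence for timing follows: "If the start date is missing or partially missing, the time of onset will be considered to be missing". The event is still analysed, attached to the last vaccination.

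SAP 4.4.1.2.4 says how. The 30-day window is defined as one "which corresponds to AEs with a time of onset between 0 and 30 days after each vaccination or missing onset date". The section adds that "An AE with missing time of onset will be considered to have occurred just after the last vaccination", and gives this as the reason for including it in those tables. It keeps a separate category in the onset display: "Time of onset period is displayed as D0-D3, D4-D7, D8-D14, D15 or later, and Missing". It also has an exclusion: "Unsolicited AEs that occurred before vaccination (negative time of onset) or with onset higher than defined above" are left out of the analysis and listed separately, with onset beyond 30 days for a non-serious AE as the example.

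SAP 4.4.1.2.3 uses the visit recorded in the *Appeared after Visit* field to choose the last vaccination when the start date is missing or partial. The trial has one vaccination.

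SAP 4.4.1.2.6 and 4.4.1.2.7 tabulate SAEs and AESIs over three periods: "Within 7 days after vaccination", within 30 days, and during the study. Neither section says what to do when onset is missing. On listings, SAP 5.3.1 says: "In all subject listings, partial and missing data will be clearly indicated as missing".

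**The concern.** A start date with month and year but no day still bounds the onset. Sometimes those bounds rule out a window altogether. The SAP has no step that uses them.

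Two things follow. First, like events are treated unlike in the 30-day tables. The exclusion for late onset needs a computable onset, so it works on a full date and cannot work on a partial one, however clear the month is. Second, the 7-day SAE and AESI counts are left to the programmer. The only placement rule in the SAP is the one that sets the event just after vaccination, and it was written for the 30-day tables.

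The 7-day figures are the ones most likely to be read as pointing to the vaccine. SAEs and AESIs should be rare in a healthy population, so a single event can make up a whole cell.

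**Working it through.** The plan states no figure on this point, so there is none to reproduce. The check is a comparison of the rules, two dated examples, and an estimate of how often the month helps.

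**Can late events exist?** SAP 3.2 collects unsolicited AEs from Day 0 to Visit 2, which falls 30 to 44 days after vaccination. Onsets on Day 31 to 44 are therefore possible, and the exclusion in 4.4.1.2.4 provides for onset beyond 30 days.

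**30-day window.** For vaccination on day *d* of a month with *m* days, a start known only to lie in the next month is at the earliest *m* − *d* + 1 days later.
- Vaccination 1 January, start recorded as February: 31 − 1 + 1 = 31. Onset is certainly after Day 30.
- Non-serious AE with a full date in February: onset is at least 31, so it is excluded and listed.
- Same AE with month and year only: onset is missing, so it is counted within 30 days.

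This result is explicit in the text and needs no inference.

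**7-day window.** Vaccination 20 January, start recorded as February: 31 − 20 + 1 = 12. Onset is certainly after Day 7. If the placement just after vaccination is applied to the 7-day SAE and AESI periods, the event is counted within 7 days. Whether it is applied there is not stated.

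**How often would month and year settle it?** Assumptions: month and year known, day unknown; every vaccination date in the planned vaccination period (Protocol 5.1.5: 15 October 2019 to 12 December 2020) equally likely; every onset day in the stated range equally likely. An event is ruled out of a window when its month is later than the month containing the window's last day.

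| True onset | Proved after Day 7 | Proved after Day 30 |
|---|---|---|
| Day 8–30 | 39% | not applicable |
| Day 8–44 | 60% | 9% |
| Day 31–44 | 94% | 25% |

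A hand check with 30-day months agrees:
- Onset on day *k* from 8 to 30 is proved after Day 7 for *k* − 7 of 30 vaccination dates. The mean of 1 to 23 is 12, and 12/30 = 40%.
- Onset on day *k* from 31 to 44 is proved after Day 30 for *k* − 30 of 30 vaccination dates. The mean of 1 to 14 is 7.5, and 7.5/30 = 25%.

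**What one event does.** Group sizes are from the Protocol synopsis; intervals are exact (Clopper-Pearson) 95%.

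| Group size | One event | No event |
|---|---|---|
| 100 (each adult group) | 1.00% (0.03 to 5.45) | 0% (0 to 3.62) |
| 233 (each paediatric group) | 0.43% (0.01 to 2.37) | 0% (0 to 1.57) |
| 466 (233 + 233, both countries) | 0.21% (0.01 to 1.19) | 0% (0 to 0.79) |

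**The case against.** The strongest defence is that the rule is written down in advance, treats all groups alike, and errs towards counting events. It touches only descriptive safety tables. It should seldom be triggered for the events that matter most: Protocol 10.1 requires SAEs to be reported within 24 hours, AESIs are collected as SAEs, start dates are among the items to be recorded, and Protocol 11.2 reconciles SAE data before the database is released. All of this stands, and it keeps the point small.

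Some stronger readings are tempting, but the documents do not support them.

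- *Every partial-date event becomes a Day 0 event.* It does not. Its onset stays missing, and the onset-period display sends it to the Missing category, not to Day 0–3.
- *Partial-date SAEs and AESIs are counted within 7 days.* The SAP does not say so. The placement sentence concerns the 30-day tables, and the sections on the 7-day periods are silent.
- *Pre-vaccination events are swept in.* SAE collection starts at vaccination (SAP 4.3.2.3.3), pre-existing conditions are not to be reported as AEs (SAP 4.3.2.1), and the visit field is consulted for partial dates. A narrow gap remains, since the negative-onset exclusion cannot act on a partial date, but such cases should be rare.
- *Listings hide the known month.* The sentence in 5.3.1 can equally mean that only the missing component is marked. It is ambiguous.
- *The month settles the matter about three times in four.* For 23 of 30 vaccination dates in a 30-day month (77%), a start in the following month is certainly after Day 7. But that is conditional on the recorded month being the following one. For true onsets on Day 8 to 30 the share is about 40%, so for most of those the month does not decide.

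**Conclusion.** The point holds as a minor one. In the 30-day tables the SAP counts partial-date events that their own recorded month shows to be too late, while excluding fully dated non-serious events with the same onset. This can affect only partial-date events starting after Day 30. Under the uniform-date assumptions, month and year would identify about a quarter of those starting on Day 31 to 44.

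For the 7-day SAE and AESI periods the defect is a missing rule. If the placement just after vaccination is used there, some later events would be counted as early ones, and month and year would correct about 40% of those truly starting on Day 8 to 30.

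The documents do not give the number of partial dates; it is assumed to be small. Whole-study SAE and AESI counts, the onset-period displays, the immunogenicity analyses and the primary conclusion do not change.

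**What to change.** In SAP 4.4.1.2.4 and 5.3.1.4, use the known part of a start date to give an earliest and a latest possible date, and then:

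- leave the event out of the 7-day or 30-day window when its earliest possible date falls after that window, keeping SAEs and AESIs in the whole-study counts;
- list the event only, as for negative onset, when its latest possible date precedes vaccination;
- otherwise keep the present conservative rule.

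State that this also governs the 7-day periods in 4.4.1.2.6 and 4.4.1.2.7, including what happens there when the start date is wholly missing. In 5.3.1, say that listings show partial dates as recorded.

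The cost is a few sentences in the SAP and a few lines of date-derivation code. No new data are needed. The downside is the minor extra programming.

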5.3.1.5 Action Taken

Missing actions taken will remain missing and not be imputed.

5.3.2 Immunogenicity

Missing data will not be imputed. No test or search for outliers will be performed.

The computational rule for undetectable responses < LLOQ and \ge ULOQ is described in Section 4.4.2.1.

5.3.3 Efficacy

Not applicable.

5.4 Interim / Preliminary Analysis

No interim / preliminary analyses are planned.

5.5 Determination of Sample Size and Power Calculation

Calculation of Sample Size:

Approximately 1332 subjects will be enrolled. An estimated 15% drop-out rate (only ages 2-17 years) from enrollment will result in approximately 1190 subjects in the per-protocol population available for immunogenicity analyses.

For the Primary Objective

With 396 evaluable subjects in the combined group (Gr5 + Gr7) and 396 evaluable subjects in the combined group (Gr6 + Gr8), the study will have 90% power using Farrington and Manning's method to declare the non-inferiority of the combined group (Gr5+ Gr7) versus the combined group (Gr6 + Gr8) based on A, C, Y, W antibodies in adolescents and children aged 2 to 17 years (assuming 15% drop-out rate for each group). The power is calculated with the assumption that the estimate from the investigational group equals that of the control group.

Table 5.2: Power of the study based on the primary objective of non-inferiority in children and adolescents aged 2 to 17 years

Antigen	Estimated* MenACYW	Estimated Menactra®	Non-inferiority	Power
A	76%	76%	10%	91%
С	94.5%	94.5%	10%	> 99.9%
Y	89%	89%	10%	> 99.9%
W	95%	95%	10%	> 99.2%
Overall				90%

Note: Evaluable subjects:

Combined group (Gr5 + Gr7) = 396 subjects Combined group (Gr6 + Gr8) = 396 subjects

Since the hypothesis needs to be met for all serogroups, no alpha adjustment for multiple comparisons is necessary in these calculations.

* Estimated seroresponses are based on the results of a study (3) conducted in India in subjects aged 2 to 75 years.

The estimates were the average of overall rates of 2 age groups (2 to 10 years and 11 to 18 years). Borrow et al. reported that incidence rates vary in RSA by province but are currently low overall (0.36/100 000 in 2014) with the majority of disease caused by MenW, followed by MenB. Approximately 66-77% of disease is caused by MenA, C, Y, or W. Due to any lack of published data from RSA it is assumed that the response in subjects aged 2-17 years will be similar between India and RSA. Additionally, any variability should balance itself out due to the wider age range.

5.6 Data Review for Statistical Purposes

A review of the data has been anticipated through the data review process led by data management before database lock. This review of the data included a statistical review.

Besides, an internal safety management team (SMT) will review the data being generated from all the ongoing studies with MenACYW conjugate vaccine at regular intervals for any new safety signals or safety concerns.

5.7 Changes in the Conduct of the Trial or Planned Analyses

In protocol, the planned analysis the primary immunogenicity analyses will be performed on the PPAS analysis set and will be confirmed on the FAS. In SAP, we change that all immunogenicity analyses will be performed on the PPAS analysis set and a supplemental analysis based on FAS will be performed to evaluate consistency of the results, If the difference between PPAS and FAS is greater than 10%. In the FAS, subjects will be analyzed by the vaccine group to which they were randomized.

For safety analyses, will include the number and percentage of subjects reporting any unsolicited AEs will be summarized, not only non-serious AEs. Unsolicited AEs includes both serious (SAEs) and non-serious unsolicited AEs.

6 References List

- 1 Newcombe R.G., Two-sided confidence intervals for the single proportion: comparison of seven methods, Statistics in Medicine, (1998) 17, 857-872.
- Newcombe RG. Interval estimation for the difference between independent proportions: comparison of eleven methods. Stat Med. 1998; 17(8):873-90.

Signature Page for VV-CLIN-0646972 v1.0 MET55_SAP_CSR_CoreBody

Approve & eSign	
	Clinical
